| UAVG | Dutch Act on Implementation of the General Data Protection Regulation; in Dutch: Uitvoeringswet AVG |
| URA | Ultrarapid acting |
| WMO | Medical Research Involving Human Subjects Act; in Dutch: Wet Medisch-wetenschappelijk Onderzoek met Mensen |

SUMMARY

Rationale: Inreda Diabetic B.V. (Goor, The Netherlands) developed a bihormonal reactive closed loop system to automate glucose regulation (artificial pancreas; AP) in patients with diabetes mellitus. In the current CE-marked AP, Humalog (Eli Lilly) is used as insulin which is a rapid acting insulin lispro. Lyumjev (Eli Lilly) also consists of insulin lispro but is ultra-rapid acting due to the addition of 2 excipients. Using Lyumjev instead of Humalog insulin could therefore result in better glycemic control.

Objective: The main objective is to determine the efficacy of Lyumjev in the Inreda AP system. Secondary objectives are: to assess safety, differences in pharmacodynamics and differences in AP-related outcome measures.

Study design: This study is a multicenter, open-labeled, randomized, cross-over trial.

Study population: The study population will be 12 patients with type 1 diabetes. The patients will be recruited from the following outpatients clinics: Rijnstate Hospital, Hospital Gelderse Vallei or Slingeland Hospital. The patients are already using the Inreda AP system.

Intervention: The intervention entails use of Lyumjev administered by the Inreda AP system. The subjects will be randomized to receive either Lyumjev or Humalog during the first study period of thirty days. After a wash-out period of eight days, the subject will be switched to the alternate treatment according to randomization.

Main study parameters/endpoints: Main parameter to express efficacy is the time above range (>10 mmol/l), which will be compared between Lyumjev and Humalog.

Nature and extent of the burden and risks associated with participation, benefit and group relatedness: There are no major risks associated with this study, since the subjects will use their usual kind of diabetes therapy, in which only the type of insulin is adjusted for thirty days. The most prominent risk is potential altered effectiveness of Lyumjev compared to the currently used insulin, which could lead to hypo- and hyperglycemia, but high and low glucose values will be indicated by alarms given by the Inreda AP system. The burden of the study is relatively low. The participants have to visit the CRC at most 2 times and the only additional burden for participants is to keep a Wi-Fi access point with them during both study periods.

1. INTRODUCTION AND RATIONALE

Over the last decade insulin delivery and blood glucose monitoring have evolved, facilitating better glucose control for patients with type 1 diabetes mellitus. Continuous subcutaneous insulin infusion and glucose sensors combined with an insulin delivery algorithm constitute a closed loop system or artificial pancreas. A closed-loop system can be categorized as mono-hormonal (subcutaneous insulin administration) or bi-hormonal (subcutaneous insulin and glucagon administration).

Inreda Diabetic B.V. (Goor, the Netherlands) developed a bi-hormonal artificial pancreas (AP) to provide automated glycemic control for insulin treated adult patients. The AP consists of two subcutaneous glucose sensors to continuously measure glucose values and an algorithm to determine the amount of insulin (Humalog, Eli Lilly) or glucagon (GlucaGen[®], Novo Nordisk) to be administered.

The AP is CE-certified in February 2020. Different clinical studies (called APPEL 1 to 5: 'Algorithm to control Postprandial, Post exercise and night glucose Excursions in a portable closed loop format') were performed to test feasibility, safety and performance. These studies facilitated market approval. The APPEL 4 study showed comparable median glucose levels for closed loop and open loop (standard insulin pump) therapy, while the time in range (3.9–10 mmol/l) was higher for closed loop [1]. Improvements were made to the prototype to allow patients to operate the system independently. Hereafter, the device was tested for two weeks in order to include multiple replacements of disposables (glucose sensors, infusion sets, and insulin- and glucagon cartridges) and observe the self-learning glucose control algorithm adapting to the individual patient (APPEL 5 study) [2]. This study demonstrated that the bi-hormonal closed-loop system provides better glycemic control than standard open loop therapy. The median time in range was higher during closed-loop (86.6% [IQR 84.9-88.3]) compared to patients' usual diabetes care (53.9% [49.7-67.2], $p < .001$) Time below range (< 3.9 mmol/l) also significantly improved during closed-loop compared to usual diabetes care (0.4% [IQR 0.1-0.8] vs 2.0% [IQR 0.7-3.6]).

The insulin used in the current CE marked AP is Humalog (Eli Lilly). Humalog is administered when glucose levels are high or increasing rapidly and reduces the occurrence of hyperglycemic events. Therefore, the performance of the AP system depends partly on the efficacy of insulin.

Humalog is classified as a rapid acting (RA) insulin. In clinical practice, type 1 diabetes mellitus patients need to administer this insulin approximately 20 minutes before meal intake to reduce postprandial hyperglycemia. The Inreda AP is a reactive system, and thus the insulin will not be administered before the meal, but will be administered when glucose levels rise rapidly. The AP results in strongly improved glycemic control compared to standard diabetes therapy, although postprandial glucose peaks are still present after the meal.

Lyumjev (Eli Lilly) is classified a ultra-rapid acting (URA) insulin. In clinical practice patients are required to administer this insulin approximately 1 minute before meal intake to reduce postprandial hyperglycemia.

Although Lyumjev insulin looks promising for the AP, Lyumjev has not yet been tested in a reactive closed-loop system. Therefore, the aim of this study is to determine the efficacy of Lyumjev in the AP.

2. OBJECTIVES

Primary Objective:

The primary objective is to determine the efficacy of Lyumjev in the AP. Main parameter to express efficacy is the time above range (>10 mmol/l). It is hypothesized that the time above range is lower using Lyumjev compared to the standard use of care: Humalog.

Secondary Objectives:

Secondary objectives are:

- to assess safety parameters;
- to assess differences in pharmacodynamics between Lyumjev and Humalog;
- to assess differences in AP-related outcomes between Lyumjev and Humalog.

3. STUDY DESIGN

Design:

This study is a multicenter, open-label, randomized, cross-over trial which will be performed in a free-living environment.

Duration:

[figure not shown]
The duration of the study per subject is 68 days. During the first thirty days the subject will be randomized to receive the first kind of insulin. After a wash-out period of eight days, the subject will receive the second kind of insulin for another thirty days according to the randomization. The following insulin formulations will be used: Lyumjev 100 units/ml in a 3 ml cartridge and Humalog 100 units/ml in a 3 ml cartridge as standard use of care.

Setting:

This study will be performed at home and patients can live according to their own daily routine. There are two study periods. Each study period lasts thirty days. The first five days of both study periods consist of a training period, which enables the investigator to optimize the settings of the Inreda AP system.

At the beginning of a study period the patient will receive the insulin cartridges according to the randomization. A wash-out period of eight days is included between the two study periods. Subjects will use Humalog during this period, as this is the standard care with the AP. Figure 3.1 shows the flow chart of the study design. During the study conduct there will be four study visits by the investigator: at the beginning and end of the intervention and control period. The training period is included to optimize the settings of the AP if necessary. This data will not be included in the analysis.

Figure 3.1 Flow chart of the study design

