4.4 Sample size calculation

It is hypothesized that the time above range is reduced in subjects using Lyumjev compared to Humalog. To detect a 3,125% (45 min per day – 15 min per meal) improvement in time spent in hyperglycemia (>10 mmol/l) with a power of 0.90 and alpha of 0.05, 10 subjects are required. To account for drop out of subjects, the sample size will be increased with 2 patients. The sample size calculation has been performed with the program G*Power 3.1.9.4. The percentage time above target range and corresponding standard deviations are based on data from the APPEL 5 study.

The following data were used to calculate sample size:

T-Test: Difference between two dependent means (matched pairs)

Alpha = 0.05

Power = 0.90

Mean 1 = 12.8

Mean 2 = 9.675

SD of mean 1 = 3.3

SD of mean 2 = 3.3

Correlation = 0.70

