8.3 Study procedures

The study starts with informing the patients about the study. If patients want to participate the informed consent form will be signed first and thereafter the patients will be screened, which can be performed online or in the CRC. The study will be performed at home and subjects can live according to their own daily routine.

At the start of the first study period the subject will receive the insulin cartridges for the first study period. After the first 30 days, there will be a washout period of 8 days where subjects will use Humalog. After the wash-out period the subjects will receive the second insulin formulation according to randomization. The same procedure as written above will be repeated. During the study conduct there will be four additional visits by the investigator: at the start and end of both the intervention and control period.

If adverse events occur during the study, the subject has to contact the investigator. If desired, an unscheduled visit could take place. If a device deficiency occurs during the study, the subject has to contact the investigator only if this is insulin-related. If there are other technical problems, the patient should follow the regular treatment protocol and contact the customer service of Inreda Diabetic B.V.

During both study periods subjects are asked to keep a Wi-Fi access point with them so researchers can assess the data if necessary. No active real-time monitoring will be performed during the study, the standard monitoring protocol will be complied. This includes monthly portal assessments and assessments at the request of the customer service.

At the start of the study the self-learning algorithm status (on or off) will not be changed. This means that the self-learning algorithm is turned on or off depending on the setting prior to the study.

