10. STATISTICAL ANALYSIS

A general description of the statistical methods to be used is given in this chapter, specific details will be provided in the Statistical Analysis Plan. The Statistical Analysis Plan will be prepared before inclusion of the first patient. Deviations from this plan should be reported in the clinical investigation report with a clear statement that this decision was made after preliminary data evaluation and thus post-hoc.

All subjects that completed both study periods will be included in the analysis. Withdrawals will be included in the analysis for adverse events and device deficiencies in order to have an adequate amount of data for analysis. Furthermore, the data collected until their withdrawal will be included in the analysis as well. Carry-over and period effects will be assessed for all parameters.

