11. ETHICAL CONSIDERATIONS

11.1 Regulation statement

This study is conducted in full accordance with the principles of the “Declaration of Helsinki” (as amended in Tokyo, Venice, Hong Kong, Somerset West, Edinburgh, Washington, Seoul and Fortaleza) [9], International Standard 14155:2020, this research protocol, the applicable SOPs and the laws and regulations of the Netherlands. The complete text of the “Declaration of Helsinki” is supplied to the investigators upon request. The study shall not begin until the required approval from the Medical Ethical Committee and approval from the CCMO following a marginal review.

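### No required check of AP settings when the insulin changes; with one sequence's glucose data excluded, the 7 participants left cannot separate insulin from period

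*Protocol*

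**What the plan says.** Protocol section 3 opens each 30-day period with five unanalysed training days, "which enables the investigator to optimize the settings of the Inreda AP system". It adds: "The training period is included to optimize the settings of the AP if necessary". On visits it says that "there will be four study visits by the investigator: at the beginning and end of the intervention and control period". The eight-day wash-out is spent on Humalog. Section 8.3 repeats the visit schedule without naming a settings task. Its one explicit rule about settings is "At the start of the study the self-learning algorithm status (on or off) will not be changed". It also states that there is no active real-time monitoring. The monitor's minimum list in section 12.2 does not name settings. The CRF (SAP 5.1.1) has a field for changes to AP settings and another for visit information, including actions decided.

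On analysis, Protocol section 10 promises: "Carry-over and period effects will be assessed for all parameters". SAP 5.3 does this by comparing the two randomization groups on the sum and on the difference of their two results. Protocol 4.4 says that "10 subjects are required", raised to 12 for dropout.

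SAP 8.1, deviation 3, reports that insulin curve and preinjection settings were adapted for Lyumjev in the Lyumjev-Humalog sequence and not returned to their pre-study values on Humalog. It calls this a procedural error, found during data analysis. AP (FCL) data of that sequence (n=5) were excluded, and other data such as adverse events were kept. Outcome parameters rest on the Humalog-Lyumjev sequence (n=7).

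**The concern.** A crossover trial protects the treatment comparison from period effects by giving the treatments in both orders. If the device's tuning differs by insulin, settings at each switch are part of the treatment. A plan that leaves them to judgement can lose the treatment contrast in one order only. That happened here: the Lyumjev-first participants ran Humalog on settings meant for Lyumjev, and their AP data were dropped.

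Only one order is left, so everything that changes between the first and second 30 days (season, routine, attention from the study, continued tuning or self-learning) is inseparable from the insulin. The check that the plan promised for this problem needs both sequences. Deviation 3 discloses the error and the 5/7 split but not this consequence. A reader who sees a randomized crossover may credit the result with a protection that the analysed data no longer have.

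**Working it through.** **Inputs.** From Protocol 4.4 and SAP 3: means 12.8 and 9.675, SD 3.3 in each condition, correlation 0.70, alpha 0.05, power 0.90. From SAP 8.1: 7 participants Humalog-first and 5 Lyumjev-first. No document gives a period drift, so D below is an assumption.

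**1. The plan's own figure.** Difference = 12.8 − 9.675 = 3.125 points. SD of the difference = 3.3 × √(2 × (1 − 0.70)) = 2.556. Standardized effect = 3.125 / 2.556 = 1.2225. Power of a paired t-test (non-central t):

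| n | two-sided | one-sided |
|---|---|---|
| 7 | 0.769 | 0.885 |
| 8 | 0.841 | 0.927 |
| 9 | 0.893 | 0.955 |
| 10 | 0.929 | 0.972 |
| 12 | 0.970 | 0.990 |

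The smallest n that reaches 0.90 is 10 two-sided and 8 one-sided. The stated 10 is therefore reproduced by a two-sided test against zero.

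**2. Precision at n=7.** The 95% CI half-width is t(0.975, n−1) × 2.556 / √n:
- n=12: 2.201 × 2.556 / √12 = 1.62 points
- n=10: 2.262 × 2.556 / √10 = 1.83 points
- n=7: 2.447 × 2.556 / √7 = 2.36 points

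The difference detectable with 90% power (two-sided) is 2.63, 2.95 and 3.78 points respectively.

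**3. Period drift.** Let D be the change from period 1 to period 2 that is unrelated to insulin. The bias in the mean of Lyumjev minus Humalog is:
- all 12, unadjusted: (7D − 5D) / 12 = 0.167D
- all 12, period-adjusted: 0, with SE = (2.556 / 2) × √(1/5 + 1/7) = 0.748, df 10, half-width 1.67 points
- the 7 Humalog-first only: 7D / 7 = D

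**4. Effect on a test.** With no insulin effect, n=7 and SD of the difference 2.556, the probability of rejection is:

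| assumed D (points) | two-sided test of zero | SAP 5.3.1 test, H0 at −3.125, drift favouring Lyumjev |
|---|---|---|
| 0.5 | 0.072 | 0.00002 |
| 1 | 0.142 | 0.0001 |
| 2 | 0.413 | 0.0035 |

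The second test reaches 0.05 only when the drift itself is 3.125 points. Likewise, if the true effect is exactly the planned 3.125 points, its power is 0.05 at any n. The power figures in step 1 therefore do not describe that test.

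**5. Planned period and carry-over tests.** Both are unpaired comparisons between sequences. With one sequence analysed there is no second group, so neither can be computed on the analysed AP data.

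**6. What randomization still supports.** Period 1 alone compares 5 on Lyumjev with 7 on Humalog. SE = 3.3 × √(1/5 + 1/7) = 1.932, df 10, half-width = 2.228 × 1.932 = 4.31 points. Two-sided power for 3.125 points is 0.31, and the difference detectable with 90% power is 6.96 points.

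**7. Opportunity to restore settings.** In the Lyumjev-first sequence, 8 wash-out days + 5 training days = 13 days on Humalog precede the first analysed day of period 2. There was time to act, but no available text obliges anyone to.

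**The case against.** **The gap is argued from an incomplete record.** The protocol points to material that is not available: "Figure 3.1 shows the flow chart of the study design", and conduct under "the applicable SOPs and the laws and regulations of the Netherlands". The standard monitoring protocol, the monitor plan, the Data Management Plan and the Data Analysis Plan were not available either. Any of them may hold a settings check. This stands, and it limits the claim to the available text.

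**The error was one of conduct.** The training window exists to tune settings, and restoring Humalog values fits naturally under a clause about necessity. A reader might infer from the sequence of events that the protocol wording caused the loss. The documents do not support that: the SAP speaks of a procedural error and attributes it to no wording. What stands is narrower. A field for recording changes does not prompt anyone when a needed change is not made.

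**The false-positive figure does not fit the SAP's test.** A reader might take 14% as the trial's error rate. It is not. It needs an assumed 1-point drift and a two-sided test of zero. Under the SAP's stated H0 the corresponding figure is about 0.0001. The bias in the estimate remains under either test.

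**The report was not seen.** Nothing shows that the limitation is missing from the clinical investigation report, so the request there is conditional. Its absence from deviation 3 can be seen.

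**The first-period comparison is weak and uses data the SAP sets aside.** Both are true. Deviation 3, however, describes the fault only after the switch back to Humalog and gives no separate reason against the period-1 Lyumjev data. SAP 5.3 itself falls back on period 1 when period 2 is unusable. That rule is triggered by a significant test, which cannot be run here, so it serves only as an analogy.

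**Visits at period start cannot verify settings tuned on days 1 to 5.** This is correct, and the fix allows for it.

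**Conclusion.** The concern holds in this form. The available protocol text allows settings to be adjusted but does not require that they be confirmed or restored when the insulin changes. After the exclusion of 5 of 12 (42%), insulin and period are fully aliased in the analysed AP data: 100% of any drift enters the estimate, against 17% in an unadjusted analysis of all 12 and none in a period-adjusted one. The tests planned in SAP 5.3 cannot be run on those data. This follows from the design and needs no outside figure.

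The loss of power is secondary: 0.77 against 0.93 two-sided (n=7 against the required 10), but still 0.88 at n=7 if the test is read as one-sided. These figures rest on the plan's SD and correlation and on a test against zero. The rejection rate of 14% (7% to 41% for drifts of 0.5 to 2 points) is illustrative, because no document gives a drift.

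A reader might go further and conclude that a period effect occurred or that the trial's result is wrong. The documents show neither; they show only that the analysed data cannot rule a period effect out. This should be fixed, mainly through reporting. Confidence is medium because of the unseen documents.

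**What to change.** **Completed trial.**
1. In SAP deviation 3, and in the clinical investigation report if it is not already there, state that the comparison comes from one sequence, cannot separate insulin from period, and could not be tested for carry-over or period effects as SAP 5.3 planned.
2. If the period-1 Lyumjev data are confirmed valid, report the randomized first-period comparison (5 Lyumjev against 7 Humalog) as a post-hoc sensitivity analysis. State its imprecision: about ±4.3 points, wider than the 3.125-point target, with power of 0.31. On its own it would settle little.

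The cost is one paragraph and one analysis. Neither recovers the lost paired data.

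**Continuation or reuse.** Amend protocol sections 3 and 8.3 to:
- record the pre-study Humalog settings at baseline;
- confirm in the CRF, at the start of period 1, the start of wash-out and the start of period 2, that the settings are those intended for the insulin in use;
- confirm them again by portal check or telephone at the end of each five-day training window, before the first analysed day.

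Which settings are right is for the clinical team. The cost is a short amendment, a few minutes per confirmation and one short remote check per period.

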13. STRUCTURED RISK ANALYSIS

13.1 Synthesis

Both the Inreda AP and Lyumjev insulin are registered and certified products. In this study both products will be used for the intended patient population and within the indication of use. Therefore, section '13.1: potential issues of concern' was omitted.

Lyumjev is not used in combination with the AP. However, Lyumjev is quite similar to Humalog and thus the Inreda AP system seems to be suitable to interact with Lyumjev insulin. Therefore, risks are minimal.

The following safety issues have to be considered.

1. It is unknown if the effectiveness of Lyumjev is completely comparable to the currently used Humalog. This could lead to hypo- and hyperglycemia, but the algorithm of the system will automatically adjust the doses, if applicable. Moreover, high and low glucose values will be indicated by alarms given by the Inreda AP system;
2. Discomfort caused by the new type of insulin. Since Lyumjev induces local vasodilation this could be more painful for the patient compared to injection with Humalog. However, diabetes patients are already familiar with the discomfort of insulin injection. These patients are therefore expected to be able to assess discomfort in advance.

In conclusion, the risks are low and most of the subjects will be already familiar with the mentioned safety issues during the management of their diabetes. The study is therefore classified as low risk. We believe that the investigational product could be an effective successor for the currently used insulin. Besides, in our opinion, the burden for the participants is acceptable.

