5.1.1 CRF Dataset

The CRF data will be collected with an eCRF implemented in *MyResearchManager*. The following data will be collected with the CRF:

- In- and exclusion criteria;
- Gold/Clarke questionnaire;
- Date of informed consent;
- Demography;
- Weight, length, HbA1c;
- Medical history;
- Randomization results;
- Visits information (including telephone contact, decided 'actions' and rationale);
- Concomitant medication;
- Adverse events;
- Device deficiencies;
- Adjustment of AP settings;
- End of study.

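### The protocol requires no check of AP settings against the insulin in use and no return to Humalog settings when Lyumjev stops; a missed reset cost the AP data of one whole sequence

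*Protocol*

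**What the plan says.** Protocol section 3 opens each 30-day period with five training days, "which enables the investigator to optimize the settings of the Inreda AP system", and repeats the purpose conditionally: "The training period is included to optimize the settings of the AP if necessary". Those days are left out of the analysis. In the eight-day wash-out participants use Humalog; nothing is said there about settings.

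Section 8.3 places the contacts: "there will be four additional visits by the investigator: at the start and end of both the intervention and control period". It gives these visits no task concerning settings. The one device setting with a written rule is self-learning: "At the start of the study the self-learning algorithm status (on or off) will not be changed". The same section rules out active real-time monitoring and keeps the usual monthly portal assessments.

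The risk analysis in section 13.1 argues that "Lyumjev is quite similar to Humalog and thus the Inreda AP system seems to be suitable to interact with Lyumjev insulin". Its first listed issue is that Lyumjev's effectiveness may differ, with dose adjustment by the algorithm and alarms as the safeguards. A mismatch between settings and insulin is not listed.

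For the analysis, protocol section 10 states: "Carry-over and period effects will be assessed for all parameters". SAP section 5.3 does this by comparing the two randomization groups. SAP section 5.1.1 lists "Adjustment of AP settings" among the CRF items.

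SAP section 8.1, item 3, reports that settings had to be adapted to Lyumjev (insulin curve and preinjection), calls the adjustments substantial, and says they were not reversed on the switch back to Humalog. It calls this a procedural error, found during data analysis. AP data from the Lyumjev-Humalog sequence (5 participants) were excluded; those from the Humalog-Lyumjev sequence (7 participants) were kept.

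**The concern.** In this cross-over the device configuration is part of the treatment. Eight days on Humalog can clear the insulin, but they do not change the settings. If settings are adapted to Lyumjev and nobody has to restore them, the next Humalog period compares Humalog under the wrong configuration. Only participants who take Lyumjev first are exposed to this, so the error follows sequence.

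The protocol had grounds to expect it. It describes Lyumjev as ultra-rapid and Humalog as rapid, provides for optimisation of settings in both periods, and notes that Lyumjev had not been tested with this system.

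What is at stake is the balance of the primary comparison. With one sequence left, insulin and period cannot be separated, and the randomized order no longer protects the time-above-range result. There is also a care aspect: participants who finish on Lyumjev go back to Humalog as usual care, and no reset is written for them either. No patient harm is recorded.

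**Working it through.** **What is required, step by step**

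| Moment | Rule on settings in the protocol |
|---|---|
| Study start | Self-learning status left unchanged |
| First five days of each period | Optimisation allowed if necessary; no target settings, no check |
| Visits at start and end of each period | None |
| Wash-out | None |
| End of Lyumjev use | None |
| External monitor's minimum checks (section 12.2) | Product identification and provision; AP settings not listed |

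The CRF item in SAP 5.1.1 records adjustments that are made; it does not require any.

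**Loss of participants.** 5 + 7 = 12, so the excluded five are the whole of one sequence. 5/12 = 0.417, or 42%. Seven remain, against 10 required (protocol 4.4 and SAP 3).

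**The plan's sample size.** Inputs from protocol 4.4: means 12.8 and 9.675 (difference 3.125 points), SD 3.3 in each condition, correlation 0.70, alpha 0.05, power 0.90.

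- SD of the paired difference = 3.3 × √(2 × (1 − 0.70)) = 2.556.
- Standardised difference = 3.125 / 2.556 = 1.223.
- Paired t-test with the noncentral t distribution, two-sided: power 0.893 with 9 and 0.929 with 10. The stated 10 is reproduced. One-sided, 8 would be enough (0.927).

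**Power and precision with the same inputs.** Half-width = t(0.975, n − 1) × 2.556 / √n.

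| n | Power, two-sided | Power, one-sided | Expected 95% CI half-width (points) |
|---|---|---|---|
| 12 | 0.970 | 0.990 | 1.62 |
| 10 | 0.929 | 0.972 | 1.83 |
| 7 | 0.769 | 0.885 | 2.36 |

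The correlation matters. At 0.5, 0.6, 0.7 and 0.8, two-sided power with 7 is 0.556, 0.649, 0.769 and 0.907; with 10 it is 0.760, 0.845, 0.929 and 0.987.

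These powers are against a difference of zero. SAP 5.3.1 tests against −3.125; if the true difference equals −3.125, power there equals alpha at any n, so the table does not describe that test.

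**Confounding with period.** Let τ be the insulin effect (Lyumjev minus Humalog) and p the effect of being in period 2. The expected paired difference is τ + p in the Humalog-Lyumjev sequence and τ − p in the Lyumjev-Humalog sequence.

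- Both sequences, simple paired mean: (7 × (τ + p) + 5 × (τ − p)) / 12 = τ + (2/12)p = τ + 0.167p. Averaging the two sequence means removes p altogether.
- Humalog-Lyumjev only: τ + p.

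The documents give no size for p, so values are assumed:

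| Assumed p (points) | Shift, both sequences | Shift, one sequence | Two-sided false-positive rate with 7 if τ = 0 |
|---|---|---|---|
| 0.5 | 0.08 | 0.5 | 0.07 |
| 1 | 0.17 | 1 | 0.14 |
| 2 | 0.33 | 2 | 0.41 |

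**Planned diagnostics.** The carry-over and period tests in SAP 5.3 compare the two randomization groups. With one group left there is nothing to compare, so neither can be run on the retained AP data.

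**The case against.** The strongest reply is that this was a lapse in conduct. A training period opened both study periods, so for the Lyumjev-Humalog sequence there were five unanalysed days on Humalog in which settings could be restored, with visits either side of the wash-out. Monthly portal assessments and CRF recording of visits and actions were also in place, and the SAP itself speaks of a procedural error. This stands in part: an intended step may have been missed. But an optional opportunity is not a requirement, and the failure covered everyone in the sequence and surfaced only at analysis.

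Second, the absence is shown for the protocol and SAP only. The Data Management Plan, the monitor plan and the standard monitoring protocol are not available here and could hold an instruction. That limit stands.

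Third, the loss has two causes. The missed reset spoiled Humalog data in period 2; dropping the same participants' Lyumjev data from period 1 was a separate decision. The SAP's own rule after a carry-over or period finding discards period 2 only, which would leave an unpaired comparison of 7 on Humalog with 5 on Lyumjev. This is a fair distinction, but it does not rescue the planned test: without valid Humalog data these five form no pairs, whatever is done with period 1.

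Fourth, the risk analysis does admit that Lyumjev's effectiveness may differ. True, but its safeguards are dose adjustment and alarms, and it does not consider settings left over from the other insulin.

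Finally, no document defines the right settings for Lyumjev, so a check on that side has no external standard. This stands. The Humalog reset does not share the problem, because its target is the participant's own pre-study settings.

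**Conclusion.** The concern holds. The protocol allows settings to be changed for Lyumjev and nowhere requires them to be checked or changed back. The SAP records that they were not changed back and that all 5 participants of one sequence (42% of the trial) were lost to the AP outcomes for that reason. Adverse event data from these five were kept.

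The confounding is the more serious consequence: the whole of any period effect now enters the comparison, against one sixth with both sequences, and it can no longer be tested. The loss of power (93% with the required 10, 77% with 7, two-sided against zero) and the wider interval (half-width 1.62 points with 12, 2.36 with 7, against a target of 3.125) come on top. Power and interval figures rest on the plan's SD of 3.3 and correlation of 0.70; the shifts rest on assumed period effects.

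The change should be made. Confidence is medium, because it is inferred that a written rule would have prevented the loss, and a rule may exist in documents not seen.

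**What to change.** Amend protocol sections 3 and 8.3; as these data are already collected, the change serves any repeat of the design.

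1. At the visits where Lyumjev starts and where it stops, the investigator checks and records the AP settings against those intended for the insulin about to be used. For Lyumjev, the intended settings are written down for each participant.
2. When Lyumjev stops, the investigator restores the pre-study Humalog settings: at the start of the wash-out for those who took Lyumjev first, at the last visit for those finishing on it.
3. At the end of each five-day training period, before the analysed days begin, the settings are confirmed once more, in the same way for both insulins.
4. All of this goes into existing CRF fields: "Adjustment of AP settings" and "Visits information (including telephone contact", the latter continuing with actions and their rationale.

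The cost is wording plus 2 × 12 = 24 checks at visits already planned and 2 × 12 = 24 end-of-training confirmations. No visit is planned at the end of training, so the confirmation would be by telephone or by whatever route is used to adjust settings. The burden is a little investigator time. If only one element is adopted, it should be the reset in item 2, which has a defined target and addresses the failure that occurred.
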